5.1 Inclusion Criteria

Participants are eligible to be included in the study only if all of the following criteria apply:

- (1) Participant is male and must be 18 years of age inclusive, at the time of signing the informed consent.
- (2) Participant has histologically or cytologically proven prostate cancer with rising PSA after failed local therapy or metastatic disease, or requiring radiotherapy, and be a candidate for long-term (i.e. >1 year) androgen deprivation therapy.
- (3) Participant requires a GnRH analogue treatment for a minimum of 18 months, of which a minimum of 3 months of GnRH analogue treatment has already been provided prior to screening. (Note: participants must receive study intervention on Day 1 in accordance with the treatment schedule of their previously received GnRH analogue therapy).
- (4) Has serum testosterone levels <1.735 nmol/L (50 ng/dL) at screening.
- (5) Has Eastern Cooperative Oncology Group (ECOG) performance status score of 0 to 1 (see Appendix 10.4).
- (6) Has a life expectancy of >18 months.
- (7) Male participants must agree that, if their partner is at risk of becoming pregnant (although highly unlikely in this study population), they will use an effective method of contraception. The participant must agree to use the contraception during the whole of the study and for 9 months after the last dose of study intervention.
- (8) Capable of giving signed informed consent as described in Appendix 10.1 which includes compliance with the requirements and restrictions listed in the informed consent form (ICF) and in this protocol.

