6.8 Concomitant Therapy

Any medication or vaccine (including over the counter prescription medicines, recreational drugs, vitamins, and/or herbal supplements) that the participant has taken within the last 2 months before or during triptorelin administration must be recorded on the eCRF along with:

- Generic or trade name
- Reason for use
- Dates of administration including start and end dates
- Dosage information including dose and frequency

The medical monitor should be contacted if there are any questions regarding concomitant or prior therapy.

The following concomitant medications are not permitted during the study:

- Finasteride or dutasteride
- Abiraterone
- Medications which are known to affect the metabolism and/or secretion of androgenic hormones: ketoconazole, aminoglutethimide, oestrogens.
- Systemic or inhaled corticosteroids (topical application permitted).
- Any herbal products previously used within 1 month prior to study start or plan to be used during the study, which are known to have cytotoxic effect or affect the metabolism and/or secretion of androgenic hormones.
- Medications known to prolong QT interval (class IA (e.g. quinidine, disopyramide) or class III (e.g. amiodarone, sotalol, dofetilide, ibutilide) antiarrhythmic medicinal products, methadone, moxifloxacin, antipsychotics).

The following concomitant medications are permitted during this study, but they must be monitored closely, and every effort should be made to keep their dose and dose regimen constant throughout the course of the study:

- Enzalutamide, apalutamide or darolutamide

- Analgesics: are allowed when necessary for pain relief.
- Anticonvulsants (e.g phenobarbital): long-term therapy may have additional risk for osteoporosis
- Other medications: any treatment which is considered necessary for the participant's welfare, may be given at the discretion of the investigator.

Other procedures: any diagnostic, therapeutic or surgical procedure performed during the study period should be recorded, including the date, indication, description of the procedure(s), and any clinical findings.

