7.2 Participant Discontinuation/Withdrawal from the Study

- A participant may withdraw from the study at any time at his own request or may be withdrawn at any time at the discretion of the investigator for safety, behavioural or compliance reasons.
- At the time of discontinuing from the study, if possible, an early discontinuation visit should be conducted, as shown in the SoA. See SoA for data to be collected at the time of study discontinuation and for any further evaluations that need to be completed.
- The reason for discontinuation will be recorded in the eCRF.
- If the participant withdraws consent for disclosure of future information, the sponsor may retain and continue to use any data collected before such withdrawal of consent.
- If the participant requests to discontinue the study intervention, they will be asked to be followed for the study procedures.
- If the participant withdraws consent for any further contact, the investigator will explain in the medical records as to whether the withdrawal is only from further receipt of study intervention or also from study procedures. This information must be entered in the eCRF.
- If a participant withdraws from the study, he may request destruction of any samples taken and not tested, and the investigator must document this in the site study records.
- A participant will be withdrawn from the study if they have inadequate testosterone suppression (defined as >50 ng/dL detected at least 30 days after the first administration of study intervention and on two consecutive measurements at least 2 weeks apart, at either a scheduled or unscheduled study visit).

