
 To demonstrate the effect of triptorelin embonate 22.5 mg 6-month formulation administered subcutaneously to suppress the 'acute-on-chronic' effect following the administration of the second dose 	
 Percentage of participants castrated on Day 3 and Day 7 after each injection administered on Day 1 and Day 169 (castration defined as testosterone <1.735 nmol/L (50 ng/dL))

 To demonstrate the effect of triptorelin embonate 22.5 mg 6-month formulation administered subcutaneously in the maintenance of PSA 	
 Percent change in PSA from baseline (prior to injection) at Day 169 and Day 337 (Percent change in PSA defined as the absolute value of difference between the PSA values at Day 169 and Day 337 and the baseline value divided by the baseline value)

Associated Procedure / Instruction Reference	319480-SOP
Form Reference	080091-FOR v7.0

Objectives	Endpoints

 To demonstrate the safety profile of triptorelin embonate 22.5mg 6-month formulation administered subcutaneously 	
 Incidence of TEAEs (including local tolerability) throughout the study i.e. up to Day 337 Change from baseline in clinical safety laboratory parameters (blood chemistry and haematology) at Day 337 Change from baseline in physical examination at Day 169 and Day 337 Change from baseline in ECG at Day 337 Change from baseline in vital signs (blood pressure and heart rate) at each visit up to Day 337

AE=adverse event; ECG=electrocardiogram; PSA=prostate-specific antigen; TEAE=treatment-emergent adverse event

Note: A list of laboratory parameters to be assessed during the study are presented in Protocol Appendix 10.2.

- Hypotheses**

Hypotheses for this study are defined below.

The primary objective of this study is to evaluate the efficacy triptorelin embonate 22.5 mg (6-month formulation) administered subcutaneously in maintaining serum testosterone castrate levels during the study (maintenance of castration defined as testosterone <1.735 nmol/L (50 ng/dL) at Day 29, Day 85, Day 141, Day 169, Day 253, Day 309 and Day 337) with two complete study intervention administrations. Thus, the null hypothesis to be tested is as follows:

Null hypothesis: percentage of participants castrated (serum level of testosterone <1.735 nmol/L) from date of first dose to Day 337 is less than or equal to 90%.

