2.3 Sample Size Determination and Power

This single-arm study is designed to demonstrate that the percentage of participants remaining castrated (maintenance of castration defined as testosterone <1.735 nmol/L (50 ng/dL) at Day 29, Day 85, Day 141, Day 169, Day 253, Day 309 and Day 337) during the study is greater than 90%. Considering an observed castration maintenance in 97% of participants, 130 eligible participants are required to demonstrate the efficacy of the triptorelin 6-month formulation with approximately 90% power and a one-sided alpha of 0.025 using an exact binomial test. The objective will be achieved if the lower bound of the 95% confidence interval (CI) of the observed rate is greater than 90%.

Considering a drop-out rate of 10%, 145 participants will be included in the study.

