5.7.2 Analysis of Primary Efficacy Endpoint

5.7.2.1 Primary Efficacy Endpoint, Treatment Effect and Estimand Definition

To assess the primary objective, the primary estimand will be defined by the following attributes:

- Population: participants with locally advanced and/or metastatic prostate cancer previously treated and castrated with a GnRH analogue as defined by the listed Inclusion/Exclusion criteria in sections 5.1 and 5.2 of the protocol, respectively.
- Variable/Endpoint: castration maintenance rate during the study defined as percentage of participants castrated (testosterone < 1.735 nmol/L (50 ng/dL)) at Day 29, Day 85, Day 141, Day 169, Day 253, Day 309 and Day 337, with two complete study intervention administrations.
- Key Intercurrent event (ICE):
 - (a) ICE 1 - Subjects discontinued from study prior to Day 337 without evidence of inadequate testosterone suppression (testosterone measurement \geq 50 ng/dL)
The testosterone values of these participants will not be considered for the main analysis (principal stratum strategy).
 - (b) ICE 2 - Subjects with at least one planned testosterone measurement missing on or prior to Day 337 without evidence of inadequate testosterone suppression (testosterone measurement \geq 50 ng/dL)
The testosterone values of these participants will not be considered for the main analysis (principal stratum strategy).

Associated Procedure / Instruction Reference	319480-SOP
Form Reference	080091-FOR v7.0

(c) ICE 3 - Subjects discontinued treatment prior to receiving the second study intervention administration without evidence of inadequate testosterone suppression (testosterone measurement ≥ 50 ng/dL)
The testosterone values of these participants will not be considered for the main analysis (principal stratum strategy).

(d) ICE 4 - Subjects received a prohibited medication during the study
Prohibited medication with impacts on the testosterone value will be identified through blinded data review. Subjects receiving identified prohibited medication (for example, finasteride, dustasteride, or abiraterone) will be included in the primary analysis as non-responder. In contrast, all testosterone measurements from subjects receiving prohibited medications other than identified ones during the study will be included in the primary analysis (composite strategy).

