5.7.2.3 Sensitivity Analysis

Sensitivity analysis for the primary estimand is intended to assess treatment effects when using different strategies. Details are listed in the following.

Estimand ID	Primary-S1	Primary-S2	Primary-S3
Estimand	Primary	Primary	Primary
Analysis Type	Sensitivity	Sensitivity	Sensitivity
Analysis Set	ITT	ITT	ITT
Variable/Endpoint	Castration maintenance rate	Castration maintenance rate	Castration maintenance rate
Intercurrent Event	Strategy		
ICE1	Subjects will be included in the analysis regardless early withdraw status (Treatment policy)	Subjects will be included in the analysis regardless early withdraw status (Treatment policy)	Subjects will be included in the analysis regardless early withdraw status (Treatment policy)

Associated Procedure / Instruction Reference	319480-SOP
Form Reference	080091-FOR v7.0

IPSEN GROUP

CONFIDENTIAL

D-FR-52014-245

SAP Final: Version 1.0: 30 January 2023

PAGE 19/43

Estimand ID	Primary-S1	Primary-S2	Primary-S3
ICE2	With analysis window being applied, subjects without 2 consecutive missing testosterone value will be included in the analysis and subjects with at least 2 consecutive missing testosterone values will be considered as non-responders (Composite policy)	Without analysis window being applied, subjects without 2 consecutive missing testosterone value will be included in the analysis and subjects with at least 2 consecutive missing testosterone values will be considered as non-responders (Composite policy)	Analysis window is not applicable. Subjects with only one missing testosterone will be included in the analysis and available testosterone values will be analyzed as observed. For subjects with at least 2 missing testosterone values and without evidence of inadequate testosterone suppression (testosterone measurement ≥ 50 ng/dL), only testosterone values prior to the first missing will be included in the analysis. For subjects with at least 2 missing testosterone values and with evidence of inadequate testosterone suppression (testosterone measurement ≥ 50 ng/dL), available testosterone values will be analyzed as observed (Composite policy)
ICE3	Subjects will be included in the analysis regardless early treatment discontinuation status (Treatment policy)	Subjects will be included in the analysis regardless early treatment discontinuation status (Treatment policy)	Subjects will be included in the analysis regardless early treatment discontinuation status (Treatment policy)

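### Replacement castration (a non-study GnRH agonist or antagonist, or orchiectomy) is named in no intercurrent event, so castrate values it produces can count as maintenance on triptorelin

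*SAP*

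**What the plan says.** **Who is enrolled and followed.** Protocol 5.1, criterion 3: "Participant requires a GnRH analogue treatment for a minimum of 18 months", of which at least 3 months must already have been given. Protocol 7.1 keeps a man who permanently stops study drug in the study for safety evaluation. Protocol 7.2 adds: "If the participant requests to discontinue the study intervention, they will be asked to be followed for the study procedures". Protocol 6.6 provides no study drug after the study ends.

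**What else he may receive.** Protocol 6.8 lists what is not permitted. One item is a class, drugs that alter androgen metabolism or secretion, followed by a colon and three entries, none of them a GnRH product. Under permitted other medications, "any treatment which is considered necessary for the participant's welfare, may be given at the discretion of the investigator". Surgical procedures are to be recorded; none is prohibited.

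**How the analysis treats it.** SAP 5.7.2.1 defines four intercurrent events. ICE4 is "Subjects received a prohibited medication during the study": drugs judged at data review to affect testosterone make the man a non-responder, and values under other prohibited drugs are kept. The named drugs are examples only. SAP 5.7.2.3 carries ICE4 unchanged into S1 to S3. For ICE3 it states in all three: "Subjects will be included in the analysis regardless early treatment discontinuation status (Treatment policy". The primary variable in 5.7.2.1 also requires two full injections.

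**The concern.** The objective is maintenance of castration by subcutaneous triptorelin 22.5 mg. A castrate value obtained under another castrating treatment carries no information about that. The trial selects men with a continuing need for GnRH therapy, so a man who stops study drug early can be expected to move to another source of castration. A man who completes both injections will need one at about the time of his final visit. The plan anticipates neither.

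S1 to S3 bring back men whom the FAS leaves out, so that the main result can be tested against their loss. If some return with castrate values caused by replacement therapy, the test is softened where it should be hardest. The plan is also uneven: ICE4 gives finasteride and abiraterone as examples of drugs that lead to non-response, while treatments that castrate directly are not mentioned.

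**Working it through.** **1. The plan's own figure.** SAP 2.3: "Considering an observed castration maintenance in 97% of participants, 130 eligible participants are required", with "approximately 90% power and a one-sided alpha of 0.025 using an exact binomial test". The null (SAP 2.1) is that the percentage castrated "from date of first dose to Day 337 is less than or equal to 90" per cent. Success (SAP 2.3) is a lower 95% limit above 90%.

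- Smallest r with P(X ≥ r | 130, 0.90) ≤ 0.025: r = 124, exact one-sided alpha 0.0207.
- Power: P(X ≥ 124 | 130, 0.97) = 0.903.
- Clopper-Pearson lower limit, the 0.025 quantile of Beta(x, n − x + 1): 124/130 gives 90.2%, 123/130 gives 89.2%.
- Drop-out: 130 / 0.90 = 144.4, rounded up to 145.

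The figures reproduce. The point concerns classification only.

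**2. How each analysis scores a man on replacement castration.** Assume no earlier value of 50 ng/dL or more; a switch after such a value does not undo the failure.

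| Case | Result under the current text |
|---|---|
| One injection, S1 | Undetermined. Analysis windows in SAP 6.1 from the Day 169 visit onward depend on the date of the second injection (D2), which he does not have. |
| One injection, S2 | No analysis windows. Can count as maintained if he has no two consecutive missing values; otherwise a non-responder. |
| One injection, S3 | Can count as maintained to Day 337 if at most one value is missing. With two or more missing, only values before the first missing one are used. |
| Two injections, complete sampling, switch before the last sample | In the FAS; can count as a responder in the primary analysis. The Day 337 analysis window starts at D2+155 and has no upper limit. |

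Two conditions apply. If the two-injection requirement in the variable carries into S1 to S3, the one-injection man fails by definition; the SAP does not say whether it or ICE3 governs. If a non-study GnRH product is held to be prohibited under 6.8 and is identified at data review, ICE4 makes him a non-responder everywhere. Neither ICE4 nor 6.8 reaches orchiectomy.

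**3. Size, by assumption.** The documents give no number of switchers. Assume all 145 men are in the ITT set and borrow the 90% bar from the primary analysis.

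- 138/145: lower limit 90.3%. 137/145: 89.4%. So at most 145 − 138 = 7 non-responders are tolerated.
- Take 4 other non-responders from any cause (97% of 130 is about 126, and 130 − 126 = 4), and k switchers who stay sampled and castrate. Counted as maintained, the result is 141/145 = 97.2%, lower limit 93.1%, whatever k is.
- Counted as non-responders:

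| k | Responders | Rate | Lower limit |
|---|---|---|---|
| 1 | 140/145 | 96.6% | 92.1% |
| 2 | 139/145 | 95.9% | 91.2% |
| 3 | 138/145 | 95.2% | 90.3% |
| 4 | 137/145 | 94.5% | 89.4% |
| 10 | 131/145 | 90.3% | 84.3% |
| 15 | 126/145 | 86.9% | 80.3% |

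With f other non-responders (f from 0 to 7), the limit falls below 90% from k = 8 − f.

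**4. A contrasting case.** If 126 of 130 completers respond and all 15 drop-outs are otherwise non-responders, the rate is 126/145, lower limit 80.3%. Counting k of the 15 as maintained lifts the limit above 90% only at k = 12 (138/145); at k = 11 (137/145) it is 89.4%. The influence of the gap therefore depends strongly on how the other drop-outs are scored.

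**The case against.** Four stronger readings are tempting, and the documents support none of them.

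- *Non-study GnRH products are not prohibited.* This is not established. The class wording in 6.8 does not say that its three entries are exhaustive, and protocol 2.2 describes GnRH agonists as suppressing testicular function. The welfare line does not clearly override a prohibited class. What stands is that these products are not named and their status is open. SAP 5.7.2.1 does not help: it points to protocol 6.3 for permitted medication, and 6.3 deals with randomisation and blinding.
- *Switchers are automatic successes.* They are not. The two-injection condition may already fail one-injection men, and the missing-value rules catch many who leave: a man who misses Days 253 and 309 is a non-responder in S2, and S3 cuts him off at his first missing value.
- *All three ITT analyses are affected alike.* S1 cannot be determined.
- *The trial's conclusion would turn on this.* Protocol 7.1 expects permanent discontinuation to be rare, 12 switchers out of 15 drop-outs would be extreme, and the SAP sets no pass rule for S1 to S3. That one man separates 123/130 from 124/130 is true of any threshold and does not show that the gap will matter.

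Treatment policy is also a legitimate strategy for a sensitivity analysis, and the primary-analysis case needs a switch before the last sample, although Day 337 is scheduled within ±3 days. Both remarks are fair. They limit the reach of the point but do not tell the analyst how to score the man when he appears, and orchiectomy remains uncovered on any reading.

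**Conclusion.** The point holds in limited form. No intercurrent event names replacement castration. Orchiectomy is outside ICE4, and the status of a non-study GnRH product under 6.8 and ICE4 is ambiguous. As written, castrate values under such treatment can count as maintenance in S2 and S3, provided sampling continues and the two-injection condition does not govern. The same can happen in the primary analysis for a two-injection man who switches before his last sample. S1 is undefined for one-injection men.

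The size is illustrative: with 145 ITT men and 4 other failures, 4 reclassified switchers move the lower limit from 93.1% to 89.4%. Both counts are assumptions, and with no switchers nothing changes. This should be corrected before database lock. It is not evidence that the sample size or the primary result is wrong.

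**What to change.** Add an intercurrent event to SAP 5.7.2.1 and 5.7.2.3: start of any non-study GnRH agonist or antagonist, or bilateral orchiectomy, after Day 1 and before the Day 337 sample. Testosterone values from that date do not count as castrate.

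- **Primary analysis (if the man is in the FAS), S1 and S2:** non-responder, by the composite strategy already used for ICE4. A replacement started only after a sample valid for the Day 337 visit leaves his status unchanged.
- **S3:** censor at that date, and show failure at that date as a second display. Calling the switch a failure outright would record a loss of castration that nobody observed.
- **One-injection men:** state whether the two-injection requirement or this event governs in S1 to S3.
- **Protocol 6.8 and ICE4:** reconcile the two texts so that it is clear whether non-study GnRH analogues are covered. This concerns how the data are classified; no clinical rule is proposed.

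The cost is SAP wording and a clarification of 6.8. Protocol 6.8 already requires dates for medication and procedures, so no new data are needed. The downside is that the ITT rates may become slightly less favourable.

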5.7.2.4 Supplementary Analysis

Primary estimand analysis will be conducted in the PP set if more than 10% of FAS subjects are excluded in the PP set.

5.7.2.5 Subgroup Analysis

The primary analysis of castration maintenance rate will be summarized within subgroups listed along with 95% exact CI in a forest plot. In the case a subgroup includes less than 20 subjects, the analysis for the given subgroup will not be carried out or combining subgroups may be considered.

- Age (<65, ≥ 65 years [65 to <75, 75 and above])
- Race (White, Black, Other)
- Baseline ECOG performance score (0, 1)

Associated Procedure / Instruction Reference	319480-SOP
Form Reference	080091-FOR v7.0

- Baseline weight (<65 kg, 65 to <85 kg, \geq 85 kg)
- Time since histological diagnose (<median, \geq median).

5.7.3 Analysis of Key Secondary Efficacy Endpoints

5.7.3.1 Secondary Efficacy Endpoints

The secondary efficacy endpoints are listed below:

- Percentage of participants castrated at each timepoint on Day 29, Day 85, Day 141, Day 169, Day 253, Day 309 and Day 337 (castration defined as testosterone <1.735 nmol/L (50 ng/dL))
- Percentage of participants with a serum testosterone level <0.694 nmol/L (20 ng/dL) during the study
- Percentage of participants with a serum testosterone level <0.69 nmol/L (20 ng/dL) at each timepoint on Day 29, Day 85, Day 141, Day 169, Day 253, Day 309 and Day 337
- Percentage of participants castrated on Day 3 and Day 7 after each injection administered on Day 1 and Day 169 (castration defined as testosterone <1.735 nmol/L (50 ng/dL))
- Percent change in PSA from baseline (prior to injection) at Day 169 and Day 337 (Percent change in PSA defined as the absolute value of difference between the PSA values at Day 169 and Day 337 and the baseline value divided by the baseline value).

